5.7.8 Duration of Treatment Based on Column Size

The duration of treatment will be summarized by column size (AKST1210 S-15, S-25, and S-35), overall AKST1210 and control at baseline, and at each scheduled post-baseline time point. The duration of each HD session in hours, the number of days of HD session, and the total duration of HD session (hours) will be summarized in each treatment period.

5.7.9 Change from Baseline in MoCA

The MoCA is a 1-page, 30-point test designed as a rapid scoring instrument for mild cognitive dysfunction. The questionnaire assesses several different cognitive domains, including attention and concentration, executive functions, memory, language, visuospatial skills, conceptual thinking, calculations and orientation. Higher scores indicate better cognitive function; the total possible score is 30 and a score of 26 or more is considered normal. Derivation for the MoCA total score = sum of individual item scores, with a range from 0 to 30.

Observed MoCA sub-scores and the MoCA summary score will be summarized by treatment group and Total at baseline, and at Visit 6 EOS. Change from baseline at Visit 6 EOS will also be summarized for sub-scores and summary score. The MoCA summary score are calculated within the EDC; this score will be obtained directly from the EDC data.

Within-group comparison of MoCA summary scores between baseline and Visit 6 EOS will be performed by Wilcoxon signed-rank test and associated P-values will be reported. Additionally, if the change in the MoCA summary score is normal based on Q-Q plot, the mean change from baseline in MoCA total score will be compared between treatment groups using an ANCOVA model with treatment as the main effect and baseline MoCA summary score as the covariate.

5.7.10 Change in Cognitive Domains by Cogstate Battery

Cogstate battery (i.e., verbal learning, psychomotor function, visual attention, working memory, executive function, and verbal delayed recall) will be assessed at Visit 1, Visit 2 Treatment Period 1 prior to HD treatment, Visit 3 Treatment Period 2, Visit 4 Treatment Period 3, Visit 5 End of Treatment, and Visit 6 EOS.

Observed scores will be summarized by treatment group and Total at baseline, and at each scheduled post-baseline time point (Visit 3 Treatment Period 2, Visit 4 Treatment Period 3, Visit 5 End of Treatment, and Visit 6 EOS for the following:

- Global Composite Score
- Episodic Memory Domain Composite Score
- Attention Domain Composite Score

- Executive Function Domain Composite Score
- Psychomotor Function
- Working Memory
- Verbal Learning

Within-group comparison of the global composite scores between baseline and each scheduled post-baseline time point will be performed by Wilcoxon signed-rank test and associated P-values will be reported. See Appendix B for instructions on composite score calculation.

Change from baseline at each scheduled post-baseline time point will be summarized. A mixed-effect model for repeated measures (MMRM) will be employed to analyze the changed scores. The model will include the fixed effects of treatment (reference=control group), baseline scores, visit (as a categorical variable), treatment by visit interaction. An unstructured covariance structure will be used to model the within subject error. Least-square (LS) means, standard error (SE), and 95% CI of the LS means will be provided for each treatment arm at each post-baseline visit. P-values testing whether the LS means at each post-baseline visit is significantly different from 0 will be provided.

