10.2 STATISTICAL HYPOTHESES

Because the primary objective of the study is safety and tolerability, the study is not designed to detect statistically significant differences between the AKST1210 column and control treatment on the efficacy endpoints. The statistical approach toward secondary efficacy endpoints will be primarily descriptive; within-subject changes from baseline for each treatment group and among-group differences will be evaluated.

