10.4 DESCRIPTION OF STATISTICAL METHODS

10.4.1 GENERAL APPROACH

Using the Evaluable Dataset, all secondary endpoints will be summarized serially over time using descriptive statistics to assess the within-subject changes and between-group differences. Overall baseline and demographic data will be summarized using descriptive statistics.

For analysis of the primary and secondary endpoints, the following will be considered:

- For endpoints that are continuous in nature:
 - Number of observations, mean, median, minimum and maximum, and standard deviation (SD) values will be presented as descriptive summary
- For endpoints that are categorical in nature:
 - Frequency counts and percentages will be presented as descriptive summary

Subject disposition (e.g., the number of subjects randomized, completed, and discontinued) will be summarized, and medical history data will be listed. Prior and concomitant medications taken from Screening and during the study will be categorized by World Health Organization classification for therapeutic class and medication name, listed and summarized by number and percentage of subjects.

Final analyses are not limited to the summaries described herein. As noted above, analytical details and assumptions will be fully presented in the SAP.

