10.4.3 ANALYSIS OF THE SECONDARY EFFICACY ENDPOINTS

The study is not powered to detect significant changes in cognition, function, etc.; however, using available data from analysis of the secondary efficacy endpoints, including changes in scores from baseline, descriptive summaries will be developed. Of particular interest will be the within-subject changes from baseline and their distribution around a null value of zero and a comparison between groups to evaluate any trends in differences between subjects randomized to active vs. control.

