4.2 Statistical Hypothesis

Because the primary objective of the study is safety and tolerability, the study is not designed to detect statistically significant differences between the AKST1210 column and control treatment on the efficacy endpoints. The statistical approach toward secondary efficacy endpoints will be primarily descriptive; within-subject changes from baseline for each treatment group will be evaluated by Wilcoxon signed-rank test. Hypothesis testing will be performed for the B2M data analysis and cognitive change based on Cogstate test battery, MoCA and PHQ-9. Please refer to the relevant sections below for details.

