5.7 Efficacy Analyses

Efficacy analyses will evaluate the feasibility of conducting expanded studies of AKST1210 in subjects with ESRD-CI who are undergoing HD 3 times per week, and its efficacy. The efficacy analyses will be descriptive only. Except where indicated, efficacy parameters will be summarized using the Evaluable and PP populations. All efficacy data, regardless of population, will be presented in data listings.

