A mixed-effect model for repeated measures (MMRM) will be employed to analyze the change from baseline b2M levels at V2.11, V3.11, V4.11 and V6. The model will include the fixed effects of treatment (reference=control group),

baseline b2M levels, visit (as a categorical variable), treatment by visit interaction, and the random effect of intercept and dialyzer types (or sites, if ≥ 5 subjects per site). Depending on the data, compound symmetry, heterogeneous compound symmetry, an unstructured covariance structure will be used to model the within subject error. Least-square (LS) means, standard error (SE), and 95% confidence interval (CI) of the LS means will be provided for each treatment arm at each visit. P-values testing whether the LS means at each visit is significantly different from 0 will be provided, which indicates the significance of AKST1210 treatment on b2M removal from baseline within group over time. The difference in LS means between treatment arms and 95% CI of the difference will also be calculated. P-value for testing whether the difference is equal to zero at all these 4 visits will be provided and compared against the alpha significance level of 0.1, which indicate significance of AKST1210 treatment on b2M removal compared to the control group.

For the second hypothesis, the null and alternative are:

$$H_0: \mu_{2C} = \mu_{2T} \text{ vs. } H_A: \mu_{2C} \neq \mu_{2T}.$$

The null hypothesis states that there is no difference in mean change (μ_2) from baseline b2M levels as measured by the changed b2M levels at sample location A prior to dialysis at V2.11, V3.11 and V4.11 in the active group. The alternative hypothesis states that there is a difference in mean change from baseline b2M levels at least in one between-visits comparison.

The same MMRM will be used. But additional LS means of three between-visit comparisons in the active group, standard error (SE), and 95% CI of the LS means will be calculated. P-value for testing whether the difference is equal to zero at all three between-visit comparisons at the active group will be provided and compared against the alpha significance level of 0.1, which indicate the significance of different AKST1210 treatment durations (and/or column sizes) on b2M removal.

For the third hypothesis, the null and alternative are:

$$H_0: \mu_{iC} = \mu_{iT} \text{ vs. } H_A: \mu_{iC} \neq \mu_{iT}.$$

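### The SAP lists no between-arm contrast for Cogstate and makes the MoCA and PHQ-9 arm comparison depend on a Q-Q plot, although the protocol asks for between-group differences

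*SAP*

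**What the plan says.** **Protocol.** Three places ask for a comparison of the arms, in descriptive terms.
- Section 10.2: "within-subject changes from baseline for each treatment group and among-group differences will be evaluated".
- Section 10.4.1: "all secondary endpoints will be summarized serially over time using descriptive statistics to assess the within-subject changes and between-group differences".
- Section 10.4.3 names as of particular interest "within-subject changes from baseline and their distribution around a null value of zero and a comparison between groups to evaluate any trends".

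**SAP, general statements.** Section 4.2 takes over the sentence from protocol 10.2 but keeps only its first half: "within-subject changes from baseline for each treatment group will be evaluated by Wilcoxon signed-rank test". It then adds: "Hypothesis testing will be performed for the B2M data analysis and cognitive change based on Cogstate test battery, MoCA and PHQ-9". Section 5.7 says: "The efficacy analyses will be descriptive only".

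**SAP, by instrument.**
- *Cogstate (5.7.10).* The model has treatment (control as reference), baseline, visit and treatment-by-visit. The listed outputs are LS means, SEs and 95% CIs for each arm, and "P-values testing whether the LS means at each post-baseline visit is significantly different from 0 will be provided". The other test, a signed-rank test on the global composite, is also within-group.
- *b2M (5.7.7).* The corresponding model does list the contrast: "The difference in LS means between treatment arms and 95% CI of the difference will also be calculated".
- *MoCA (5.7.9) and PHQ-9 (5.7.12).* A within-group signed-rank test is always done. The between-arm ANCOVA is done only if the change score is judged normal on a Q-Q plot.
- *SF-36, PSQI and FACIT (5.7.11, 5.7.13, 5.7.14).* There are by-arm summaries and within-group signed-rank tests, but no estimated arm difference. PSQI and FACIT add a Fisher's test on a proportion without naming the groups compared.

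**The concern.** Every subject is tested repeatedly, and all move to a reduced flow rate with longer sessions. Practice, time and the changed dialysis regimen can shift scores in both arms. The concealed control is there so that such shared change can be subtracted. A p-value against zero in the active arm does not subtract it: the rejection may be correct as a statement about that arm and still say nothing about the column. A result in which one arm is significant and the other is not is easily misread as a device effect.

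SAP 4.3 expects trends in these endpoints to inform the size of later studies. The effect needed for that is the randomised difference and its uncertainty, not one arm's change from baseline.

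For MoCA and PHQ-9, the plan could end with no between-arm estimate, depending on a visual judgement with no stated threshold. The check is also applied to the change score, whereas the ANCOVA assumption concerns the residuals.

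**Working it through.** **1. Inputs from the documents.** Ten evaluable subjects per arm, 1:1 (protocol summary and 10.5); two-sided 0.05 (SAP 5.1); four post-baseline Cogstate visits (SAP 5.7.10). The enrolment figure reproduces: 20/(1 − 0.20) = 25 against about 26 planned, and 26 × 0.80 = 20.8, or about 20 evaluable. It is not in dispute.

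**2. Assumptions.** The documents give no SD, no visit correlation and no expected shift for any cognitive score. I assume normal data, complete follow-up, no device effect, a correlation of 0.6 between visits, and a shift common to both arms of 0, 0.2, 0.3 or 0.5 SD of the change score.

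**3. How often each test rejects at one visit.** The MMRM is as in 5.7.10 (unstructured covariance, REML, t with 17 df, 4,000 trials). The one-visit ANCOVA has treatment and baseline (40,000 trials). The signed-rank test is exact and applied to the active arm.

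| Shared shift (SD) | MMRM: active LS mean vs 0 | MMRM: arm difference | ANCOVA: active LS mean vs 0 | ANCOVA: arm difference | Signed-rank, active arm |
|---|---|---|---|---|---|
| 0 | 4.8% | 4.2% | 4.8% | 4.9% | 4.9% |
| 0.2 | 9.3% | 4.8% | 8.9% | 4.9% | 8.4% |
| 0.3 | 13.8% | 5.2% | 14.4% | 5.0% | 13.0% |
| 0.5 | 30.5% | 5.3% | 31.3% | 5.1% | 28.4% |

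Sensitivity at 0.3 and 0.5 SD, one visit, active LS mean against zero:
- 10 per arm, baseline-change correlation −0.4: 17.1% and 36.5%.
- 8 per arm, correlation 0: 12.2% and 24.9%.
- 8 per arm, correlation −0.4: 14.6% and 29.7%.

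The arm difference stays between 4.9% and 5.2%.

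**4. Exactly one arm significant.** For independent arms with rejection probability p, this is 2p(1 − p). With the signed-rank figures: 2 × 0.130 × 0.870 = 0.226 at 0.3 SD and 2 × 0.284 × 0.716 = 0.407 at 0.5 SD. A separate simulation of 20,000 trials gives 23% and 40%, against 9% with no shift.

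**5. Precision of the missing contrast (95% half-widths, in SD of the change).**
- 10 per arm, difference: t(17) × √(2/10) = 0.944. One arm's LS mean: t(17) × √(1/10) = 0.667. One-sample interval: t(9)/√10 = 0.715.
- 8 per arm, difference: t(13) × √(2/8) = 1.080. One arm's LS mean: t(13) × √(1/8) = 0.764.

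**6. The Q-Q condition.** A visual check has no error rate, so a Shapiro-Wilk test at n = 20 stands in for it, for illustration only. It fails in about 5% of samples when the change is normal, in 9% to 16% when a normal change is rounded to integers (SD 3 to 2), and in 34% to 84% for the heavy-tailed or skewed distributions tried. In those cases no between-arm estimate of MoCA or PHQ-9 is specified. The rank-sum test is named only for demographics (SAP 5.4.1). The log transformation for non-normal residuals is named only for b2M (5.7.7), and an optional transformation only for the non-card-based Cogstate tests (5.9).

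**The case against.** The protocol asks for description and disclaims power, and the SAP delivers much of that description. Results are presented by arm. The Cogstate arm difference is the subtraction of two reported LS means from one model, and combining their SEs recovers its SE closely: with complete data at one visit and 10 per arm, the median ratio is 0.994 and the 5th percentile 0.95. On this view only an output line is missing, and the table shells, which are separate files not seen here, may contain it. That describes how small the repair is; it does not remove the need. The SAP announces hypothesis testing for Cogstate, MoCA and PHQ-9, and for Cogstate the listed p-values answer the less useful question.

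The 14% to 31% is the power of a one-arm test to detect an assumed shift, not an error rate of the plan. This is correct. Two familiarization runs precede the Cogstate baseline (protocol 7.1.1.3.3), so the shift may be small, and the fair range starts at about 5%. Those runs do not cover MoCA or PHQ-9.

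SAP 5.1 allows changes for unanticipated features of the data. That is not a prespecified fallback.

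For SF-36, PSQI and FACIT the objection largely stands. By-arm summaries partly meet protocol 10.4.1, no testing is announced for them in SAP 4.2, and Fisher's test compares arms elsewhere in the SAP (5.4.1, 5.8.5.2), so between-arm is its natural reading. This is a lesser point of consistency.

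**Conclusion.** The concern holds. Followed as written, the listed Cogstate inference cannot separate a device effect from shared change, and MoCA and PHQ-9 may end with no between-arm estimate. The protocol asks for that comparison in three places, and the b2M section of the same SAP already shows the wording.

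With no device effect, the active arm is significant against zero at a given visit in about 5% of trials with no shared shift, 9% at 0.2 SD and 14% to 31% at 0.3 to 0.5 SD. The arm difference stays at about 5%. These figures rest on the assumed shift, normal data and complete follow-up. The textual gap does not depend on them.

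This should be corrected, but nothing confirmatory depends on it and the primary safety endpoint is untouched.

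**What to change.** - **Cogstate (5.7.10):** add the AKST1210-minus-control LS-mean difference with 95% CI at each post-baseline visit, from the model already specified, and make it the main result.
- **MoCA and PHQ-9 (5.7.9, 5.7.12):** run the ANCOVA whatever the Q-Q plot shows, and name a rank-based or permutation between-arm analysis as a check.
- **SAP 4.2 and 5.7:** restore the among-group clause, reconcile the descriptive-only statement with the announced testing, and label within-arm p-values as descriptive.
- **For consistency:** report a baseline-adjusted arm difference with 95% CI for SF-36 MCS and PCS, PSQI total and FACIT score, and name the groups in the Fisher's tests.

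The cost is SAP wording and a few contrast statements, with no new data. The intervals will be wide: about ±0.94 SD at 10 per arm and ±1.08 SD at 8, against ±0.67 and ±0.76 SD for one arm's LS mean. The results therefore support estimation only, and the report should say so.

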5.7.11 Change in Quality of life using Short-Form Health Survey (SF-36)

The SF-36 yields 8 scales and 2 summary scores for mental health (MCS) and physical health (PCS). SF-36 will be assessed at Visit 2 Treatment Period 1 prior to HD treatment, Visit 3 Treatment Period 2, Visit 4 Treatment Period 3, Visit 5 End of Treatment, and Visit 6 EOS.

Scores from the eight scales (i.e., physical functioning (PF), role physical (RP), bodily pain (BP), general health (GH), vitality (VT), social functioning (SF), role emotional (RE), and mental health (MH)), as well as the summated MCS and PCS will be summarized by treatment group and Total at baseline and at each scheduled post-baseline time point. Change from baseline at each scheduled post-baseline time point will also be summarized.

Within-group comparison for both the MCS and PCS scores between baseline and each scheduled post-baseline time point will be performed by Wilcoxon signed-rank test and associated P-values will be reported.

[figure not shown]
The eight scales will be calculated using the RAND method available from the RAND website https://www.rand.org/health-care/surveys_tools/mos/36-item-short-form/scoring.html.

The MCS and PCS will be scored using the norm-based scoring methods based on the SF-36® summary measures manual ([Jenkinson et al., 1998](#)) in three steps.

AKST1210-201

SAP Rev. B

A listing of SF-36 assessments, including the summary scores for mental and physical health, will be provided.

5.7.12 Change in Patient Health Questionnaire-9 (PHQ-9)

Scores will be summated for each subject across the 9 items and the calculated total score will be summarized by treatment group and Total at baseline, and at Visit 6 EOS. Within-group comparison of calculated total scores between baseline and Visit 6 EOS will be performed by Wilcoxon signed-rank test and associated P-values will be reported. Change from baseline at Visit 6 EOS will also be summarized. A listing of PHQ-9, including the total score, will be provided.

Additionally, if the change PHQ-9 total score is normal based on Q-Q plot, the mean change from baseline in PHQ-9 total score will be compared between treatment groups using an ANCOVA model treatment with treatment as the main effect and baseline PHQ-9 total score as the covariate.

5.7.13 Change in Sleep Quality, Measured by Pittsburgh Sleep Quality Index (PSQI)

The PSQI differentiates “poor” from “good” sleep by measuring 7 domains: subjective sleep quality, sleep latency, sleep duration, habitual sleep efficiency, sleep disturbances, use of sleep medication, and daytime dysfunction over the last month. The subject self-rates each of these 7 areas of sleep. Scoring of the answers is based on a 0 to 3 scale, whereby 3 reflects the negative extreme on the Likert Scale. A global sum of “5” or greater indicates a “poor” sleeper. PSQI will be assessed at Visit 2 Treatment Period 1 prior to HD treatment, Visit 3 Treatment Period 2, Visit 4 Treatment Period 3, Visit 5 End of Treatment, and Visit 6 EOS.

Scores will be summated for each subject across all items. The calculated total score, the number and percentage of subjects who are considered “poor” sleepers, and the scores for each domain will be summarized by treatment group and Total at baseline and at each scheduled post-baseline time point. See Appendix C for instructions on the calculation of total score. Change from baseline in the total score and for each domain at each scheduled post-baseline time point will also be summarized.

Within-group comparison of the total score between baseline and each scheduled post-baseline time point will be performed by Wilcoxon signed-rank test and

associated P-values will be reported. A fisher's exact test will be used to compare the proportion of subjects considered "poor" sleepers.

A listing of PSQI, including the total score and a variable identifying if a subject is a poor sleeper, will be provided.

5.7.14 Change in Fatigue, Measured by Fatigue Questionnaire – Functional Assessments of Chronic Illness Therapy (FACIT)

The level of fatigue is measured on a 4-point Likert scale (4 = not at all fatigued to 0 = very much fatigued). The score ranges from 0 to 52. A score of less than 30 indicates severe fatigue. The higher the score, the better the quality of life. FACIT-Fatigue subscale will be assessed at Visit 2 Treatment Period 1 prior to HD treatment, Visit 3 Treatment Period 2, Visit 4 Treatment Period 3, Visit 5 End of Treatment, and Visit 6 EOS.

The fatigue subscale score, and the number and percentage of subjects with severe fatigue will be summarized by treatment group and Total at baseline and at each scheduled post-baseline time point. Change from baseline in the fatigue subscale score at each scheduled post-baseline time point will also be summarized.

Within-group comparison of the fatigue subscale score between baseline and each scheduled post-baseline time point will be performed by Wilcoxon signed-rank test and associated P-values will be reported. A fisher's exact test will be used to compare the proportion of subjects with severe fatigue.

A listing of FACIT, including the fatigue subscale score and a variable identifying if a subject has severe fatigue, will be provided.

5.8 Safety Analyses

Safety analyses include hemodialysis parameters, adverse events, laboratory parameters, vital signs, weight, 12-lead electrocardiogram (ECG), physical examination, pregnancy tests, cognitive assessments during IDH and prior and concomitant medications. Except where indicated, safety parameters will be summarized by treatment group (AKST1210 and Control) using the safety population. A subset of the safety tables defined below will also be provided to the

DSMB for their periodic assessment of safety. The DSMB tables are identified within the analysis description.

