8.5 STUDY HALTING RULES

The Data and Safety Monitoring Board (DSMB) will make recommendations concerning the continuation, modification, or termination of the trial.

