5.7.1 Feasibility of all Procedures

Feasibility of all procedures will be determined by the number of assessments that can be completed by the subject, visits that are completed, dialysis sessions that are completed with the longer dialysis time and the number of times the dialysis session becomes unblinded to treatment. A less than 75% completion by subjects would determine the procedure non-feasible calculated by treatment period and study overall. The percentage of subjects who are missing at each procedure will also be summarized.

5.7.2 Tolerability of Column Size, including Subject Compliance with Visit Completion, Procedures, Subject Retention

The number and percentage of subjects will be summarized by column size (AKST1210 S-15, S-25, and S-35), overall AKST1210 and control for the following:

- Subjects entered into each treatment period
- Subjects who de-escalated to a lower column size in treatment period 3 categorized by reason: IDH only, Anemia only, IDH and Anemia. Anemia is defined as having a hemoglobin (Hgb) lab value of < 9g/dL, Subjects who were discontinued due to treatment or HD
- Subjects who completed all the visits

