5.7.3 Change in IDH Rate Above Historical IDH Rate for Column Size

The number and percentage of subjects will be summarized by column size (AKST1210 S-15, S-25, and S-35), overall AKST1210 and control for the following:

- Historical IDH Rate (0,1,2,3,4)
- Number of IDH (0,1,2,3,4,5, 6)
- Change in IDH Rate above the Historical IDH Rate (0,1,2, 3)

A listing of IDH Rate, including each subject's historical IDH rate and number of hypotensive events, will be provided.

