5.7.4 Incidence of IDH Leading to De-escalation or Discontinuation

The number and percentage of subjects with any IDH leading to de-escalation or discontinuation from AKST1210/control will be summarized by treatment group and Total.

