5.8.5.3 Adverse Events Leading to Withdrawal

A summary of incidence rates (frequencies and percentages) of TEAEs leading to withdrawal of study device, by treatment group, SOC, and PT will be prepared for Safety Dataset. No inferential statistical tests will be performed.

A data listing of AEs leading to withdrawal of study device provided, displaying details of the event(s) captured on the CRF.

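### The SAP marks no table of IDH counts, worsening anemia, de-escalation or device withdrawal for the DSMB, so the Board's marked tables show IDH and low hemoglobin by arm but not event counts, column size or treatment changes

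*SAP*

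**What the plan says.** SAP 5.8 sets the DSMB's package by a marking system. "A subset of the safety tables defined below will also be provided to the" DSMB, and "The DSMB tables are identified within the analysis description". The default layout is by arm: "Except where indicated, safety parameters will be summarized by treatment group (AKST1210 and Control) using the safety population".

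The outputs that bear most directly on column-size decisions are mostly in SAP 5.7, the efficacy section. For 5.7.4 the plan is: "The number and percentage of subjects with any IDH leading to de-escalation or discontinuation from AKST1210/control will be summarized by treatment group and Total". Section 5.7.2 tabulates "Subjects who de-escalated to a lower column size in treatment period 3 categorized by reason: IDH only, Anemia only, IDH and Anemia". Within 5.8 itself, the section on adverse events leading to withdrawal plans "A summary of incidence rates (frequencies and percentages) of TEAEs leading to withdrawal of study device". (SAP 5.8 uses the number 5.8.5.3 twice; the second use, for deaths, is marked for the DSMB.)

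Protocol Appendix 17.1 bases escalation and de-escalation on IDH events relative to each subject's Expected IDH Rate in a 4-week period and on an Hgb limit of 9 g/dL. On halting, Protocol 8.5 says only that the DSMB "will make recommendations concerning the continuation, modification, or termination of the trial".

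**The concern.** IDH and anemia are the two risks on which the escalation rules turn, and the outputs that describe them in the form those rules use are not marked for the DSMB. Four of the six are specific to IDH or anemia (5.7.3 to 5.7.6), one counts de-escalations by reason (5.7.2), and one counts device withdrawals for adverse events.

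Protocol 10.4.2 evaluates the primary endpoint through TEAEs and through AEs leading to de-escalation or discontinuation, with AE tables by arm and column size. So the unmarked outputs belong to the trial's main safety question even though most of them are filed under efficacy.

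If the marks are followed literally, the Board could see similar proportions of subjects with any IDH in the two arms while event counts, step-downs or withdrawals differed. The sponsor and CRO physicians who review data between meetings work from blinded cumulative data (Protocol 8.6), so that review would not show a difference between arms.

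**Working it through.** **Step 1. Which outputs are marked.** Reading SAP 5.7 and 5.8 line by line:

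| Output | SAP section | DSMB mark |
|---|---|---|
| Hemodialysis listing | 5.8.1 | yes |
| All TEAEs by SOC/PT | 5.8.5.1 | yes |
| Serious TEAEs | 5.8.5.2 | yes |
| Deaths listing | 5.8.5.3 (second use) | yes |
| Laboratory data | 5.8.6 | yes |
| Vital signs | 5.8.7 | yes |
| Weight | 5.8.8 | yes |
| ECG | 5.8.9 | yes |
| Prior and concomitant medications | 5.8.13 | yes |
| Column tolerability, de-escalation by reason | 5.7.2 | no |
| IDH counts and change from historical rate | 5.7.3 | no |
| IDH leading to de-escalation or discontinuation | 5.7.4 | no |
| Worsening anemia | 5.7.5 | no |
| Anemia leading to de-escalation or discontinuation | 5.7.6 | no |
| TEAEs leading to device withdrawal | 5.8.5.3 (first use) | no |

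Nine outputs are marked, all in 5.8. None of the six outputs in question is.

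**Step 2. What reaches the Board by another route.**

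- *IDH.* Appendix 17.1 requires every IDH after consent to be recorded as an AE. IDH after first treatment therefore enters the marked TEAE table, which is by SOC, PT and treatment group (SAP 5.8.5, 5.8.5.1).
- *Anemia.* The marked laboratory output gives Hgb values, change from baseline, and the number and percentage of subjects beyond the flag limits. The Hgb flag is below 9 g/dL, the same value as in Appendix 17.1.
- *Column size.* SAP 5.1 says listings carry the column size for each treatment period where applicable. The marked hemodialysis listing should therefore show it subject by subject.

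**Step 3. What does not.**

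- *IDH event counts.* SAP 5.8.5.1 counts a subject once per PT, so repeat events do not show. The listing of all AEs in that section, from which counts could be rebuilt, carries no mark of its own.
- *De-escalations and their reasons.* The AE form's action-taken field offers only no action or device discontinued (Protocol 8.4.1), so a step down in column size cannot be read from it.
- *Summaries by column size.* None of the marked descriptions calls for one.
- *Device withdrawals for TEAEs.* These appear only in the unmarked table.
- *Anemia over time.* By-visit denominators are subjects with data at that visit (SAP 5.1), so a subject who stops for anemia drops out of later visits in the laboratory table.

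**Step 4. How much a subject-once table can hide.** Assume that a subject with Historical IDH Rate h per 8 weeks keeps a constant Poisson rate over 12 weeks. The expected count is h × 12/8 = 1.5h, and 3h if the rate doubles. The chance of at least one IDH is 1 − exp(−1.5h), against 1 − exp(−3h).

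| h | Expected events, unchanged → doubled | P(≥1 IDH), unchanged | P(≥1 IDH), doubled | Difference |
|---|---|---|---|---|
| 1 | 1.5 → 3 | 0.777 | 0.950 | 17 points |
| 2 | 3 → 6 | 0.950 | 0.998 | 4.7 points |
| 3 | 4.5 → 9 | 0.989 | 0.9999 | 1.1 points |
| 4 | 6 → 12 | 0.998 | 0.99999 | 0.2 points |

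The event count doubles in every row, while the proportion of subjects with any event barely moves from h = 2 upward. At h = 0 a doubling has no meaning, but any new IDH registers as a new subject, so the subject-once table is at its most sensitive there. The documents do not give the distribution of h, so no figure for the whole arm can be derived.

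**Step 5. Whether marking alone would be enough.** It would not. SAP 5.7 tables default to the Evaluable and PP populations, and Evaluable requires a Week 8 visit (SAP 5.2.3). A subject stopped before Week 8 for IDH or anemia would be missing from them. Section 5.7.2 also counts de-escalations in treatment period 3 only, whereas the Protocol 15.1.3 schedule already monitors for de-escalation throughout period 2.

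**The case against.** The strongest reply is that the Board already sees both risks. IDH is in the marked TEAE table by arm, Hgb below 9 g/dL is in the marked laboratory table by arm, and intradialytic blood pressure and the hemodialysis listing are marked too. With about 26 subjects, a careful reader of the listings could work out who was not escalated or was stepped down. This stands in large part. A reader might infer from the missing marks that the DSMB would not see IDH or anemia by arm at all; the documents do not support that. What the reply does not supply is a table of IDH event counts, reasons for de-escalation, or device withdrawals.

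A second reply is that the charter decides. Protocol 8.6 and SAP 4.9 say it will define each data element the Board needs, and the table shells are separate files. This also stands: the gap is shown for the SAP's marking, not for the package the Board actually receives.

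Third, a reader might take the DSMB to be the only body able to stop the trial. It is not. It makes recommendations, and Protocol 5.5 lets the sponsor terminate at any time, with an unacceptable emerging safety profile as a listed reason. Sponsor and CRO physicians can also trigger an ad-hoc meeting. However, their ongoing review is of blinded data, so it does not replace a comparison by arm.

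Fourth, the Poisson figures leave out Historical 0, ignore de-escalation or discontinuation after excess IDH, and say nothing about anemia or withdrawals. This is fair. They illustrate one limitation of one table and do not show that a doubling would be hidden across an arm.

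**Conclusion.** The point holds in a limited form. Six outputs that describe IDH burden, worsening anemia, treatment changes and device withdrawals carry no DSMB mark in the SAP. The marked tables give the by-arm proportion of subjects with IDH and with Hgb below 9 g/dL, but not event counts, reasons for de-escalation, column-size summaries or device withdrawals.

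The size can be stated only for IDH and only by stratum: a doubled rate shifts 12-week subject incidence by about 17 points at Historical 1 and by under 5 points at Historical 2 to 4. This assumes a constant Poisson rate equal to the historical one and no change of treatment during the 12 weeks. Nothing can be said for the arm as a whole without the mix of historical rates. The conclusion also rests on the SAP's marks defining the package; a charter that lists these elements would close the gap.

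This is worth correcting because it is a cheap improvement to safety oversight. It is not evidence that the Board is uninformed about either risk.

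**What to change.** 1. Add the DSMB-report mark to SAP 5.7.2, 5.7.3, 5.7.4, 5.7.5, 5.7.6 and the section on adverse events leading to withdrawal (5.8.5.3, first use).
2. State that the DSMB versions are cumulative, by arm (and by column size where the SAP already plans it), and on the Safety population in place of the Evaluable and PP default.
3. In 5.7.2, count de-escalations and their reasons in every treatment period where they can occur, not only in period 3.
4. List the same outputs in the DSMB charter so that the two documents agree.

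No escalation, de-escalation or discontinuation rule changes. The cost is more than wording: the 5.7 tables need Safety-population versions, 5.7.2 needs a wider count, and the set has to be run for each DSMB meeting, which Protocol 8.6 puts at quarterly or more often. For a trial of about 26 subjects that is modest programming.
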